6.5. Extent of Exposure

Extent of exposure to GSK2857916 will be summarized.

The number of cycles administered to study treatment will be summarised with mean, median, standard deviation, minimum, and maximum. The number and percentage of subjects who received a given number of cycles (<4, 4, and >4 cycles) will be reported.

Dose intensity (dose delivered per cycle) will be summarized using mean, median, standard deviation, minimum, and maximum by cycle and overall. Dose intensity is the cumulative actual dose divided by the total number of cycles across the entire treatment period. A by subject summary listing of data on exposure to all study treatments will be produced.

Dose reductions will be summarised by number of reductions and reasons for reductions. Dose delays will be summarised by number of delays, reasons for the delays, and delay duration (days). The number and percentage of the delays 1-21, 22-42 and >42 days will be computed. Primary reasons for dose reductions and dose delays will also be summarized by cycle.

Duration of delays is defined as period from the expected start date of dose to actual start date of current dose. Calculation: (actual start date of current dose - expected start date of dose). Expected start date of dose = actual start date of previous dose + 21.

The summaries of dose modifications will be provided only if the data warrant.

All the dose reductions, dose escalations, infusion interruptions, incomplete infusions and dose delays will be listed separately.

A plot showing the number and percentage of subjects treated at different dose levels over time will be provided.

The duration of exposure to study treatment in days (from first day to last day of treatment) will be calculated. A horizontal bar graph of duration of treatment will be produced that displays duration of treatment in days for each subject.

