9.1.2. Derived Pharmacokinetic Parameters

9.1.2.1. Non-compartmental Analysis

- The pharmacokinetic parameters for Part 1 will be calculated by standard non-compartmental analysis according to current working practices and using Phoenix WinNonlin, version 6.3 or later.
- All calculations of non-compartmental parameters will be based on actual sampling times.
- Pharmacokinetic parameters described in [Table 7](#) will be determined from the Cycle 1 plasma concentration-time data in Part 1 of the study separately for each analyte, as data permit.

Table 7 Derived Pharmacokinetic Parameters

Parameter	Parameter Description
AUC(0-t)	Area under the concentration-time curve from time zero to the time of the last quantifiable concentration (C(t)) will be calculated using the linear trapezoidal rule for each incremental trapezoid and the log trapezoidal rule for each decremental trapezoid.
AUC(0- τ)	Area under the concentration-time curve during the dosing interval
AUC(0- ∞)	Area under the concentration-time curve extrapolated to infinity will be calculated as: AUC = AUC(0-t) + C(t) / lambda_z
%AUC _{ex}	The percentage of AUC (0- ∞) obtained by extrapolation (%AUC _{ex}) will be calculated as: [AUC(0-inf) – AUC(0-t)] / AUC(0-inf) x 100
C _{max}	Maximum observed concentration, determined directly from the concentration-time data for each cycle. For cys-mcMMAF, C _{max} will not be derived when only predose and EOI samples were collected.
t _{max}	Time to reach C _{max} , determined directly from the concentration-time data for each cycle
C _{τ}	Trough concentration prior to the next dose for each cycle

Parameter	Parameter Description
Ctrough	
$t_{1/2}$	Apparent terminal half-life will be calculated as: $t_{1/2} = \ln 2 / \lambda_{z}$
tlast	Time of last observed quantifiable concentration
CL	Clearance
Vss	Volume of distribution at steady state
λ_z , λ_{z}	Terminal phase rate constant
Ae(0-t)	Urinary recovery of cys-mcMMAF within t hours after start of infusion will be calculated as: $\text{Urine cys-mcMMAF concentration} \times 24\text{-h urine volume}$ t = time from start of infusion to end of urine collection period (≤ 24 h)
Fe(0-t)	Fraction of cys-mcMMAF dose excreted within t hours after start of infusion will be calculated as: $Ae(0-t) / \text{cys-mcMMAF dose}$

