For the purpose of accumulation ratio analysis, CEOI at each cycle will be used. Preliminary analysis found that cys-mcMMAF Cmax did not occur at or near EOI in most cases; therefore, the cys-mcMMAF accumulation ratio based on CEOI is not based on Cmax.

Accumulation ration will only be derived and analyses will only be performed for subjects who received at least 80% of the planned dose at cycle 1. $Ro(CEOI) = CEOI_{Cx D1} / CEOI_{C1 D1}$;
 $x = 3, 5$;

$Ro(Ctrough) = Ctrough_{Cx D1} / Ctrough_{C1 D1}$;
 $x = 4$;

Only one accumulation ratio for CEOI and Ctrough will be derived for each subject according to the rules below:

Preliminary pharmacokinetic data indicate that the pharmacokinetics for the third consecutive dose given at the planned interval will be at steady state. Therefore, based on the study design, subjects who meet one of the following criteria will be at steady state

When assessing accumulation ratio based on CEOI:

- Subjects who receive the same dose without delay or change for Cycles 1, 2, and 3 (i.e., with dosing delays of ≤ 3 days). In this case, Cycle 3 represents steady state. Accumulation ratios are calculated as Cycle 3/Cycle 1.
- Subjects who have a dose reduction or two by Cycle 3, but then dose is maintained at the same level and interval through Cycle 5. Cycle 5 represents steady-state pharmacokinetics, but dose adjustment is needed. Dose adjustment: multiply CEOI values by the ratio (starting dose level/Cycle 3-5 dose level). Accumulation ratio = adjusted Cycle 5/Cycle 1.

When assessing accumulation ratio based on Ctrough:

- Subjects who receive the same dose without delay or change to Cycle 4 (i.e., with dosing delays of ≤ 3 days). Accumulation ratio = Cycle 4 Ctrough/Cycle 1 Ctrough.
- Subjects who have a dose reduction by Cycle 2, but then dose is maintained at the same level and interval through Cycle 4. Cycle 4 represents steady-state pharmacokinetics, but dose adjustment is needed. Dose adjustment: multiply Ctrough values by the ratio (starting dose level/Cycle 2-4 dose level). Accumulation ratio = adjusted Cycle 4 Ctrough/Cycle 1 Ctrough.

Accumulation ratios of CEOI and Ctrough will be summarised using descriptive statistics by planned initial dose level, graphically presented (where appropriate) and listed.

9.3.1.3. Assessment of Analyte Ratios:

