For the purpose of analyte ratio analysis, CEOI at each cycle will be used, and Ctrough is defined as the concentration immediately prior to the next cycle dose. Preliminary analysis found that cys-mcMMAF Cmax did not occur at or near EOI in most cases; therefore, the cys-mcMMAF analyte ratio based on EOI is not based on Cmax.

Analyte Ratios of CEOI and Ctrough are defined as the ratio of CEOI and Ctrough for analytes: unbound antibody, total antibody, and cys-mcMMAF to CEOI and Ctrough for analyte ADC at each cycle:

Ratio of analytes at each cycle versus ADC at Cycle X:

$$Ra \text{ (CEOI)} = \frac{\text{CEOI (unbound antibody, total antibody, cys-mcMMAF) Cycle X}}{\text{CEOI (ADC) Cycle X}}$$

X = 1, 2, 3, 5;

$$Ra \text{ (Ctrough)} = \frac{\text{Ctrough (unbound antibody, total antibody, cys-mcMMAF) Cycle X}}{\text{Ctrough (ADC) Cycle X}}$$

X = 1, 2, 4;

To fit into the analysis model, the units of the analytes need to be converted from ng/mL or pg/mL to nM as below.

	Original unit	Operation	Converted unit
ADC	ng/mL	/152.1	nM
Total Antibody	ng/mL	/152.1	nM
Unbound Antibody	ng/mL	/152.1	nM
cys-mcMMAF	pg/mL	/1045	nM

Analyte ratios of CEOI and Ctrough for each will be summarised using descriptive statistics by planned initial dose level and cycle, graphically presented (where appropriate) and listed.

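### The eligibility rules for the trough accumulation ratio do not control when its two samples are drawn: the Cycle 1 trough is unlimited on the reduced-dose path, and the delay limit on the unreduced path, read literally, stops before the Cycle 4 trough

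*SAP*

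**What the plan says.** Section 9.3.1.2 sets Ro(Ctrough) as the Cycle 4 trough divided by the Cycle 1 trough, one value per subject, and gives two ways to qualify.

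- **Unreduced path:** "Subjects who receive the same dose without delay or change to Cycle 4 (i.e., with dosing delays of ≤ 3 days").
- **Reduced path:** "Subjects who have a dose reduction by Cycle 2, but then dose is maintained at the same level and interval through Cycle 4". The adjustment is to "multiply Ctrough values by the ratio (starting dose level/Cycle 2-4 dose level").

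Both rest on the premise that "the pharmacokinetics for the third consecutive dose given at the planned interval will be at steady state".

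Table 7 (Section 9.1.2.1) defines Ctrough as "Trough concentration prior to the next dose for each cycle". Section 9.3.1.3 agrees: "Ctrough is defined as the concentration immediately prior to the next cycle dose". Both Part 2 every-3-weeks schedules (Sections 16.2.3.1 and 16.2.3.3) list pre-dose PK samples on C1D1, C2D1, C3D1 and C5D1, and none on C4D1.

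Section 6.5 counts a delay from the previous dose plus 21 days and plans delay categories: "The number and percentage of the delays 1-21, 22-42 and >42 days will be computed".

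**The concern.** The delay conditions match the logic of the end-of-infusion ratio, whose sample is taken on the day of the last dose named. A trough is timed by the dose that follows it. A condition that stops at the Cycle 4 dose therefore need not control the Cycle 4 trough. A condition that starts only after a reduction does not control the Cycle 1 trough.

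A trough drawn late is lower because more drug has been eliminated. If it is the numerator, the subject appears to accumulate less; if it is the denominator, more. Both kinds of subject enter the same summaries with a 95% CI (for Part 2 MM, tables 4.0161, 4.0171 and 4.0191) and the same plot of geometric means with a reference line at 1 (figure 14.0141).

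**Working it through.** **Which samples are used.** The Ctrough definitions make the Cycle 1 trough the C2D1 pre-dose sample and the Cycle 4 trough the C5D1 pre-dose sample. The programming note for figure 14.0180 uses the same rule: the pre-dose value of one cycle is the trough of the cycle before. The formula label in Section 9.3.1.2 (Cx D1 with x = 4) could be read as C4D1 pre-dose, but Part 2 schedules no such sample.

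**Which intervals are controlled.**

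| Path | Cycle 1 to 2 (times the denominator) | Cycle 4 to 5 (times the numerator) |
|---|---|---|
| Unreduced | Covered by the 3-day limit | Not covered if the limit runs only to the Cycle 4 dose |
| Reduced | No limit | Depends on whether the interval through Cycle 4 includes the one ending at Cycle 5 |

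**Whether another rule closes the gap.** Section 16.3 applies no assessment windows. The dose adjustment rescales for dose level only. Section 9.1.2.1 bases non-compartmental calculations on actual sampling times, but an observed trough is the measured value whatever time is recorded with it.

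**Size.** The SAP gives no accumulation ratio or half-life, so there is no figure to reproduce. Assumptions:

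- One-compartment superposition with 21-day dosing.
- Half-life h of 7, 14 or 19 days for ADC or antibody. The upper end comes from the SAP's premise: if the third dose reaches at least 90% of steady state, h is at most 63 / log2(10) = 19.0 days.
- Reduced-to-starting dose ratio f of 0.74 (2.5/3.4), chosen only for illustration. The adjustment largely cancels it.

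Let r = 2^(-21/h), and x = 2^(-d/h) for a delay of d days.

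- Unreduced, on schedule: Ro = 1 + r + r² + r³. With h = 14, r = 0.354 and Ro = 1.52.
- Unreduced, Cycle 5 late by d: Ro is multiplied by x. With h = 14 and d = 7, x = 0.707 and Ro = 1.08.
- Reduced, Cycle 2 late by d and later doses on time: Ro = (1 + r + r²)/x + r³/f. With h = 14 and d = 7, Ro = 1.479/0.707 + 0.044/0.735 = 2.15, against 1.54 on schedule.

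| h (days) | Unreduced, on schedule | Cycle 5 late 7 d (factor) | Cycle 5 late 21 d | Reduced, on schedule | Cycle 2 late 7 d (factor) | Cycle 2 late 21 d |
|---|---|---|---|---|---|---|
| 7 | 1.14 | 0.57 (0.50) | 0.14 | 1.14 | 2.28 (2.00) | 9.13 |
| 14 | 1.52 | 1.08 (0.71) | 0.54 | 1.54 | 2.15 (1.40) | 4.24 |
| 19 | 1.78 | 1.38 (0.77) | 0.83 | 1.82 | 2.31 (1.27) | 3.75 |

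The direction is the same at every half-life; only the size changes. If both samples of a reduced-path subject are late by the same amount, the errors nearly cancel: with h = 14 and both 7 days late, Ro is 1.52 against 1.54.

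**The case against.** **The unreduced-path gap depends on the reading.** The reduced path speaks of the interval through Cycle 4, and that can be taken to include the interval ending at C5D1. The unreduced wording, "Subjects who receive the same dose without delay or change to Cycle 4", may be loose rather than an omission. This stands, so that half is a literal reading that needs clarifying. It does not help the reduced path, where neither reading limits the Cycle 1-to-2 interval.

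**The SAP has a general provision.** Section 16.5.2 says the effect of major departures from planned assessment times will be assessed as appropriate, and it puts planned and actual times in listings. Section 9.3.1.2 also lists individual ratios. A late trough would therefore be visible, but it would still be derived and summarised.

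**Little depends on the result.** The ratios are descriptive, are produced only if data are sufficient, and drive no test, stopping rule or sample size. The planned population PK work on myeloma ADC data uses actual time since infusion. All of this stands and limits the importance of the point.

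**Stronger readings that a reader might infer.**

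- *Delays come from toxicity, so the error is systematic.* Section 6.5 says only that reasons for delays will be summarised. The display list plans tables of adverse events leading to interruptions or delays. Neither shows why, or how often, delays occur.
- *Long delays are expected.* The Section 6.5 categories are table bins, and those summaries are produced only if the data warrant.
- *The ratio measures scheduling rather than accumulation.* That could be true only of subjects with a late sample.
- *The same size applies to cys-mcMMAF.* It is a different molecule (1045 Da against 152.1 kDa), and nothing in the SAP supports using the same half-life range for it.

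**Conclusion.** The point holds in a limited form. The missing limit on the Cycle 1-to-2 interval of the reduced path is firm: a subject whose Cycle 2 dose was both late and reduced qualifies, and the ratio is inflated. The Cycle 4-to-5 gap on the unreduced path follows from the literal wording and lowers the ratio.

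The size rests on the assumed 7 to 19 day half-life and the one-compartment model. For a sample 7 days late, an individual ADC or antibody ratio is multiplied by about 0.50 to 0.77 (late Cycle 5) or about 1.3 to 2.0 (late Cycle 2). The documents do not say how many subjects would be affected. Because the two errors run in opposite directions, a claim that the summary is biased in a known direction is not supported. The consequence is confined to a secondary, descriptive PK analysis.

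**What to change.** Add to both paths in Section 9.3.1.2: Ro(Ctrough) is derived only if the Cycle 1 and Cycle 4 troughs were each drawn within 3 days of the planned 21 days after the start of the preceding infusion (18 to 24 days, by recorded times); otherwise it is not derived and the subject is listed. This uses the 3-day tolerance already in the section and settles the meaning of to and through Cycle 4. It restricts which data enter an analysis and leaves dosing untouched.

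The work is one eligibility line. The population PK dataset specification (Section 16.9.1) already derives time since the most recent infusion and counts it from the previous cycle for pre-dose samples. The cost is that fewer subjects contribute a trough ratio. Some error remains inside the window: a sample exactly 3 days late still multiplies a ratio by 0.74, 0.86 or 0.90 (late Cycle 5), or by 1.35, 1.15 or 1.11 (late Cycle 2), at half-lives of 7, 14 and 19 days.

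Model-predicted troughs at exactly 21 days are not a suitable substitute. The population PK dataset leaves out unbound antibody and lymphoma subjects, and a prediction would replace the observed ratio that the section defines.

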9.3.2. Model Checking & Diagnostics

Endpoint(s)	
 • For Dose Proportionality Analysis (Part 1), Log_e-transformed single dose PK parameters as defined in Section 9.3.1.1, as applicable.
Analysis	
 • Mixed Effects

Assumptions:
 
 • Model assumptions will be applied, but appropriate adjustments may be made based on the data. • The Kenward and Roger method for approximating the denominator degrees of freedom and correcting for bias in the estimated variance-covariance of the fixed effects will be used. • An unstructured covariance structure for the G matrix will be used by specifying 'type=UN' on the RANDOM line. 
 ○ In the event that this model fails to converge, alternative correlation structures may be considered such as VC or CS. ○ Akaike's Information Criteria (AIC) will be used to assist with the selection of covariance structure. • Distributional assumptions underlying the model used for analysis will be examined by obtaining a normal probability plot of the residuals and a plot of the residuals versus the fitted values (i.e., checking the normality assumption and constant variance assumption of the model respectively) to gain confidence that the model assumptions are reasonable. • If there are any departures from the distributional assumptions, alternative models will be explored using appropriate transformed data. 	

10. POPULATION PHARMACOKINETIC (POPPK) ANALYSES

The primary goal of this analysis is to characterize the population pharmacokinetics of GSK2857916 and associated analytes after intravenous of GSK2857916 in participants with multiple myeloma, data permitting. The influence of subject demographics, baseline characteristics including disease activity, and other covariates on the pharmacokinetics of GSK2857916 will be investigated. The individual subject pharmacokinetic parameters will be estimated and documented for the purposes of any subsequent exposure-response (PK/PD) analyses. This analysis will be performed by CPMS and reported separately.

A summary of the planned population pharmacokinetic analyses is outlined below:

- Plasma concentration-time data for GSK2857916 ADC will be subjected to nonlinear mixed effects modelling using the program NONMEM to develop a population pharmacokinetic model. A similar approach may be used on the data from two analytes (ADC and cys-mcMMAF) and three analytes (ADC, total antibody, and cys-mcMMAF) together.
- Individual *post hoc* estimated pharmacokinetic parameters will be summarized descriptively.
- To support this analysis, a population PK dataset will be generated. The details for the dataset specifications are provided in [Appendix 9: Population Pharmacokinetic \(PopPK\) Analyses](#).

Detailed population PK methodology is presented in [Appendix 9: Population Pharmacokinetic \(PopPK\) Analyses](#).

**11. PHARMACODYNAMIC (AND / OR BIOMARKER)
ANALYSES**

The pharmacodynamic analyses will be documented in a separate RAP.

12. PHARMACOKINETIC / PHARMACODYNAMIC ANALYSES

12.1. Exposure-Response for Efficacy and Corneal Events

The primary goal of this analysis is to characterize the pharmacokinetic/pharmacodynamic relationships for GSK2857916 administered IV in subjects with multiple myeloma for efficacy and corneal events, data permitting. In these analyses, drug plasma concentration (or pharmacokinetic parameter) data and pharmacodynamic data will be subjected to logistic regression and time-to-event analysis, as appropriate, using suitable software. The influence of subject demographics and baseline characteristics, including disease activity, in this population may be investigated. Detailed PK/PD methodology is provided in [Appendix 10: Pharmacokinetic / Pharmacodynamic Analyses](#). This analysis will be performed by CPMS and reported separately.

12.2. Concentration-QTc Analyses

For each ECG assessment, the individual subject's QTcF change from baseline will be calculated and will be merged with time-matched PK concentration values for the timepoints at which they are available. QTcF change from baseline (y-axis) will be plotted against the PK concentration data (x-axis) separately for each analyte (ADC, unbound mAb, total mAb, and cys-mc-MMAF). If appropriate, linear regression analyses may be performed for each analyte- Δ QTcF plot.

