5.2. Baseline Definitions

For all endpoints (except as noted in baseline definitions) the baseline value will be the latest pre-dose assessment with a non-missing value, including those from unscheduled visits. If time is not collected, Day 1 assessments are assumed to be taken prior to first dose and used as baseline.

For subjects who did not receive study treatment during the study, baseline will be defined as the latest, non-missing collected value.

For ECG analyses, subject level baseline is defined as the mean of triplicate baseline assessments.

Unless otherwise stated, if baseline data is missing no derivation will be performed and baseline will be set to missing.

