5. On initial (first infusion) dosing day, vital signs must be assessed at pre-dose (within 30 minutes prior to SOI), +10 minutes, +30 minutes (\pm 15 min) after SOI, EOI, and 1 hour post EOI. On subsequent dosing days, vital signs must be assessed at pre-dose (within 30 minutes prior to SOI), +30 minutes after SOI, and EOI. **On days where vital sign timepoints align with PK sampling timepoints, vital signs should be assessed prior to PK samples being drawn.**
6. If completed within 72 hrs prior to the first dose, this assessment need not be repeated on Day 1 of Cycle 1. Refer to Table 15 of the protocol for a comprehensive list of lab tests.
7. Troponin will be measured at the local (troponin I or T) and central (troponin I) lab.
8. CK-MB at the local lab or if not available by a central laboratory.
9. BNP to be measured locally, or if not available by a central laboratory, at screening; if cardiac workup is required due to safety concerns during the study, BNP should be measured.

10. Perform only in women of child-bearing potential. A serum pregnancy test should be performed at screening, and subsequent pregnancy tests may be either serum or urine.
11. Final pregnancy test (serum or urine) must be performed in women of childbearing potential 60 days after last study treatment.
12. ECGs to be performed in triplicate. On dosing days, ECG to be performed at predose (within 30 minutes prior to SOI) and EOI. At screening, on interim visits (C1D8 and C1D15) and End of Study, obtain a single ECG measurement. **On days where ECG timepoints align with PK sampling timepoints, ECGs should be performed prior to PK samples being drawn (PK sample should be taken at the exact nominal time; refer to footnote 24)**
13. At Screening, LVEF may be performed within 30 days prior to first dose. All ECHOs indicated on dosing days may be performed up to 5 days before dosing. ECHOs to be done locally and sent to GSK for central imaging storage.
14. May be performed up to 21 days prior to C1D1 as screening value. Needs to be performed with the same method throughout the study as was done at baseline (i.e. if PET scan was used as baseline, subject needs to be followed by PET scans). Selected target lesion needs to be measured and followed over time.
15. Samples from within 14 days prior to first dose are acceptable.

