16. Sample(s) collected for analysis at central lab. The same sample will be used for BCMA (flow) and PD. On D8 only postdose PD assessment will be performed, if applicable (refer to footnote 18).
17. FISH testing at least for: t(4;14), t(14;16), 17p13del. FISH results from samples taken within 60 days prior to first dose are acceptable.
18. **Additional samples may be collected in some subjects (up to 6) for further exploration of PD.**
19. Archival tissue from up to 60 days prior to study is acceptable.
20. Collect sBCMA at C1D1 predose (within 30 minutes prior to SOI) and at EOI (± 5 minutes), C2D1 at predose (within 30 minutes prior to SOI) and at EOI (± 5 minutes).
21. Collect cytokines at predose (within 30 minutes prior to SOI) and EOI (± 5 min) (even when infusion is interrupted or halted) to assess allergic reaction
22. All ADA samples will be collected prior to each infusion
23. Flow cytometry performed central laboratory.
24. PK samples to be taken for both GSK2587916 and cys-mcMMAF measurement on C1D1, C2D1, C3D1, and C5D1 at predose (within 30 minutes prior to SOI) and at EOI (just before EOI).
25. Collect 1 PK sample at each subject's final visit.
26. Informed consent for optional genetics research should be obtained before collecting a sample.
27. Study drug administration ± 3 day window only.
28. Prophylaxis with prednisolone phosphate 1% or dexamethasone 0.1% 1 drop QID x 4 days starting 1 day prior to treatment
29. All participants should be followed for survival for 1 year from last subject last dose. and whether subsequent treatment for disease was given. Subject does not need to come in for visit. Participants who have completed treatment or the 3 month follow up visit (end of study) prior to amendment 5 will be reconsented for further follow up and survival status.
30. e-Diary to be completed at screening, then Days 1-7, 8, 15 of each treatment cycle. Upon implementation of the e-Diary, these assessments will be required.
31. OSDI and NEI-VFQ-25 to be administered during end of study treatment visit. Additional assessments for subjects who are experiencing corneal symptoms to be completed via telephone on a monthly basis for up to 1 year, or until resolution of symptoms (whichever comes first) during the follow-up period.
32. Exit interview to be performed within 21 days of end of study visit

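### Section 12.2 permits an optional regression of QTcF change on concentration over repeated values per subject without a term for subject, so any standard error or interval taken from it would be invalid

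*SAP*

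**What the plan says.** **The analysis.** Section 12.2 derives one QTcF change from baseline per ECG assessment. Each is "merged with time-matched PK concentration values for the timepoints at which they are available". Then "QTcF change from baseline (y-axis) will be plotted against the PK concentration data (x-axis) separately for each analyte" (four analytes). The only modelling sentence is conditional: "If appropriate, linear regression analyses may be performed for each" plot. No subject effect, test, confidence interval or decision rule is given.

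**The data.** For Part 2 myeloma (section 16.2.3.1) the ECG footnote reads: "On dosing days, ECG to be performed at predose (within 30 minutes prior to SOI) and EOI". The PK footnote puts samples on "C1D1, C2D1, C3D1, and C5D1 at predose (within 30 minutes prior to SOI) and at EOI", plus one at the final visit. By section 5.2, the "subject level baseline is defined as the mean of triplicate baseline assessments", so all of a subject's changes share it.

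**The displays.** Section 16.12.12 lists one plot per analyte for MM and one for NHL. The end-of-study list (section 4.1.7) has All Treated plots with disease colour-coded, for three of the analytes. Section 4.1.9 adds NHL listings. No table of slopes or predicted changes appears in the lists available.

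**The contrast.** For dose proportionality, section 9.3.1.1 does specify a subject random effect, and section 9.3.2 adds Kenward-Roger degrees of freedom.

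**The concern.** A regression run on a plot whose points are assessments, with no subject term, treats several values from one person as independent. They are not: they share the person and the subtracted baseline. If a slope or a predicted QTcF change were reported from such a fit, its precision would be misstated. For a concentration-QTc assessment that matters both ways. Too small a slope standard error can produce a false signal, and too narrow an interval for the predicted change can give a falsely reassuring upper limit. Leaving the subject structure open also means that it would be settled after the data are seen.

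**Working it through.** The SAP states no figure on this point, so there is none to reproduce.

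**1. Pairs per subject** (Cycle 1 Day 1 pre-dose taken as baseline)
- Part 2 MM (section 16.2.3.1): EOI on C1D1 (1), pre-dose and EOI on C2D1, C3D1 and C5D1 (3 × 2 = 6), final visit (1). Total 8.
- Part 1 (section 16.2.2.1): EOI on C1D1 (1), C1D8 and C1D15 (2), pre-dose and EOI on C2D1 and C3D1 (4), final visit (1). Total 8.

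Subjects who stop early contribute fewer.

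**2. Correlation from the shared baseline.** Suppose a baseline triplicate mean and a post-dose triplicate mean have the same error variance v, with independent errors. Then Var(Δ) = v + v = 2v, and two changes from one subject have covariance v. Their correlation is v/2v = 0.5. This is an illustration: the documents give no variances. It shows why independence cannot be assumed even though each subject's stable level has been subtracted.

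**3. Effect on a pooled fit.** With m values per subject, correlation ρ of the changes and within-subject correlation ρx of the concentrations:

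- true variance of slope / variance assumed by the pooled fit ≈ 1 + (m − 1) ρ ρx
- the same ratio for the fitted value at the mean concentration ≈ 1 + (m − 1) ρ

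The slope error can go either way, because ρx is negative when concentration varies mainly within subjects. The fitted-value error goes one way for any positive ρ. With m = 8 and ρ = 0.2, 0.4, 0.6, the second ratio is 2.4, 3.8, 5.2. The standard error is then too small by √2.4 = 1.55, √3.8 = 1.95 and √5.2 = 2.28. A nominal 90% interval has true limits of 1.645/1.55 = 1.06, 1.645/1.95 = 0.84 and 1.645/2.28 = 0.72 standard errors, hence coverage of about 71%, 60% and 53%.

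**4. Simulation of the slope test** (true slope 0, nominal two-sided 5%, 1,500 runs per setting). From the SAP: doses 0.03 to 4.6 mg/kg (section 5.1), 40 Part 2 MM subjects at 3.4 mg/kg (section 2.3), 8 pairs each. Assumed: 35 Part 1 subjects, between-subject log-SD of concentration 0.3, within-subject log-SD 0.15, and the trough/EOI ratios and correlations shown.

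| Data | Trough/EOI | Type I error at ρ = 0.3 / 0.5 / 0.7 | Pooled SE ÷ true SD |
|---|---|---|---|
| Pooled MM | 0.05 | 0.059 / 0.091 / 0.095 | 0.94 / 0.87 / 0.84 |
| Pooled MM | 0.3 | 0.143 / 0.174 / 0.196 | 0.76 / 0.69 / 0.65 |
| Pooled MM | 0.8 | 0.229 / 0.313 / 0.372 | 0.60 / 0.52 / 0.45 |
| Part 2 MM only | 0.05 | 0.048 / 0.040 / 0.029 | 1.04 / 1.06 / 1.11 |
| Part 2 MM only | 0.3 | 0.084 / 0.079 / 0.114 | 0.89 / 0.87 / 0.81 |
| Part 2 MM only | 0.8 | 0.203 / 0.297 / 0.371 | 0.64 / 0.54 / 0.47 |

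Check against step 3 at ρ = 0.5. In the pooled MM design with ratio 0.3, ρx is about 0.31, so the variance ratio is 1 + 7 × 0.5 × 0.31 = 2.09 and 1/√2.09 = 0.69, as simulated. In Part 2 MM with ratio 0.05, ρx is about −0.04, giving 1 − 7 × 0.5 × 0.04 = 0.86 and 1/√0.86 = 1.08, against 1.06 simulated.

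**5. Predicted change.** For pooled MM with ρ from 0.2 to 0.6 and ratios from 0.05 to 0.8, the slope test rejected about 7% to 35% of the time. The nominal 90% interval at the assumed 3.4 mg/kg EOI concentration covered 53% to 78%. Standard errors clustered by subject brought these to about 5–6% and 88–90%.

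**The case against.** A reader might infer that the SAP prescribes ordinary least squares and that its confidence intervals and p-values are too optimistic. The documents do not support that:

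- The regression is doubly optional, and neither ordinary nor simple appears in section 12.2. A mixed model is not excluded.
- There are no planned intervals or p-values to be optimistic. The listed outputs are plots and NHL listings, whereas dose proportionality has a 90% interval and a results table. The mock shell for these plots is not in the text available, so what would be drawn on them cannot be checked.
- The direction is not certain. In Part 2 MM alone with a trough/EOI ratio of 0.05, the slope test rejected at 3% to 5%, that is, at or below nominal.
- If subject effects are unrelated to concentration, a pooled line is unbiased. Subtracting a baseline is not an error in itself.
- The sizes rest on correlations and concentration profiles that the documents do not give.
- QTcF safety does not depend on this fit. Section 8.7 plans worst-case grade increases, the 31–60 and >60 msec change categories, a shift plot and a listing.

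All of this stands, and it limits the severity. It does not remove the gap. The only method named is a linear regression on a plot of assessments, and nothing tells the analyst to account for subject. The conservative cases also lie outside the listed myeloma plots: no plot of Part 2 MM alone is listed, and the MM and All Treated plots span the full dose range, where much of the concentration variation is between subjects.

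**Conclusion.** The point holds as an under-specified, optional, exploratory analysis, at low severity. If the regression is run as literally worded and a slope standard error or an interval for the predicted change is reported, that measure of precision is invalid. For the pooled MM plots it is generally too narrow, with the type I error and coverage given in step 5. The All Treated plots should behave similarly, since they add at most 10 lymphoma subjects at 3.4 mg/kg, though they were not simulated separately. For a single-dose cohort such as NHL with low troughs, the slope test may be slightly conservative. The interval for the predicted change would still be too narrow under any positive within-subject correlation, at least near the mean concentration. The direction and size depend on the assumed correlations and trough/EOI ratios. That the pooled standard errors are not valid follows from the data structure alone.

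**What to change.** In section 12.2, replace the reference to linear regression with: *a linear mixed-effects model of QTcF change from baseline on concentration, with a random subject intercept, and a random slope if it converges*. Add that any reported slope or predicted QTcF change will be given with a 90% confidence interval from that model. Kenward-Roger degrees of freedom can be carried over from section 9.3.2, which helps with up to 10 lymphoma subjects. The fit may stay optional, and if only plots are produced nothing else changes. The cost is one sentence in the SAP, minor programming on the same data, and intervals that will usually be somewhat wider.
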